4.4. Study Days and Visits

Study days will be numbered relative to the first day of IMP administration (i.e., the first administration in Period 1). The start of treatment (Day 1) is defined as the date for which a patient receives the first dose of study drug, as recorded on the Case Report Form (CRF). Days will be numbered relative to treatment start (i.e., ..., -2, -1, 1, 2, ...; with Day 1 being the first day of study drug administration and day -1 being the day before the first day of study drug administration).

In case the Early Termination (ET)/End-of-Treatment (EOT) visit occurred on the allowed time window for any scheduled visit (according to Table 1 and Table 2 of the study protocol), and the scheduled visit results are missing, the results from the overlapping ET/EOT visit will be mapped to the scheduled visit.

In case the EOT or Follow-up visit assessments were collected out of the allowed time window, assessment results will be excluded from the by-visit summary tables but will be included in relevant listings. In addition, if there are multiple assessments at a post-baseline visit day, then the last non-missing assessment at that visit will be used, unless otherwise specified.

For the by-visit summary tables, only scheduled visits, EOT and follow-up visits will be presented. The ET visit will not be presented, and unscheduled visits will not be mapped or presented. For the 'at any time' summary statistics in the shift tables and in the presentation of Potentially Clinically Significant (PCS) summaries, all visits will be used (including unscheduled visits).

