10.8. Tolerability Analysis

All-cause discontinuation rates and discontinuation rates due to adverse events (dropout rates) will be calculated as the number of patients who withdrew early for all reasons, and the number of patients who withdrew early due to adverse events, respectively, divided by number of patients in each treatment group, and will be presented using descriptive statistics.

Time to all-cause discontinuation will be calculated as the discontinuation date minus the randomization date plus 1. Kaplan-Meier curves for the time to discontinuation as a result of all causes will be plotted.

Tolerability analyses will be performed on the safety analysis set by treatment group and period.

10.9. Pharmacokinetic, Population Pharmacokinetic, Pharmacodynamic, and Pharmacokinetic/Pharmacodynamic Analysis

Plasma concentrations will be tabulated at each planned sampling time point by treatment group.

In addition, the pharmacokinetics of TV-44749 will be evaluated using a population pharmacokinetics approach. [REDACTED]

Importantly, independent pharmacokinetic and population-based modeling analysis will take place during the study conduct, while maintaining the blind during Period 1, as will be described in the separate predefined unblinded pharmacokinetic analyses plan. Pharmacodynamic data from Period 1 will not be shared before database lock and unblinding for the efficacy analysis.

[REDACTED]

[REDACTED]

[REDACTED]

[REDACTED]

[REDACTED]

The population pharmacokinetic/pharmacodynamic analysis of relevant pharmacodynamic variables and/or exposure-response analysis of relevant efficacy or safety endpoints may be performed and reported in a separate pharmacometrics report.

Samples collected at 2.5 to 3 hours post IMP administration will not be analyzed routinely during the study but rather only in the event of potential PDSS that will be evaluated by the IDMC.

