3.3. Safety Analysis Set

The safety analysis set for Period 1 will include all randomized patients who received at least 1 dose of TV-44749 or placebo. The safety analysis set for Period 2 will include all randomized patients to Period 2 who received at least 1 dose of TV-44749. For the integrated study periods summary tables (see Section [8](#)) the safety analysis set will include all patients in the safety analysis set of period 1 that received 1 of the 3 TV-44749 treatments groups, or all patients that meet the definition of the safety analysis set of Period 2.

In each of the safety analysis sets, treatment will be assigned based on the initial treatment patients actually received in the corresponding period, regardless of the treatment to which they were randomized, and regardless of dose adjustments, unless otherwise specified. For the integrated periods summary tables, patients randomized in Period 1 to 1 of the 3 TV-44749 groups will be counted according to the initial dose they actually received in Period 1. Patients that were randomized to Placebo in Period 1 will be counted according to the initial dose of TV-44749 they actually received after the re-randomization of those patients to the 1 of the 3 TV-44749 treatment groups in Period 2, regardless of dose adjustment that may occur during Period 2.

In cases of dosing error, a decision of what is the treatment assignment for these patients will be made in a blinded manner prior to unblinding of Period 1, as applicable. The decision will be made during the statistical data review meeting and will be documented in the statistical data review document.

For IDMC monitoring during the study, the safety analysis set will use the treatment based on the randomization assignment in the opening of each period.

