4.2. Specification of Baseline Values

For Period 1, the baseline value for a patient is the last observed data that was collected for this patient prior to the first IMP dose administration, unless otherwise noted.

For Period 2, the baseline value for a patient is the last observed data that was collected for a patient prior to the third IMP administration (i.e., first administration in period 2, at visit 11, week 8), unless otherwise specified (see procedures and assessments which may be performed after the re-randomization to Period 2 at visit 11 in Section 6.9.1 in the study protocol).

For the integrated periods to be presented in the CSR and during the IDMC closed (in an unblinded manner) and open (in a blinded manner) sessions, the baseline values of patients initially randomized in Period 1 to TV-44749 groups will be defined as the last observed data that was collected prior to the first TV-44749 dose administration. For patients that were assigned to placebo group in Period 1, the baseline value is the baseline value for Period 2 (see above paragraph).

It should be noted that the baseline values of placebo patients will differ between tables presented in the integrated periods summaries and those presented in Period 1 summaries.

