8. SAFETY ANALYSIS

8.1. General

Safety analyses will follow the safety estimand approach using the safety analysis sets.

Safety will be assessed by qualified study personnel by evaluating reported adverse events (including serious adverse events, extrapyramidal symptoms, injection pain, injection site findings and Injection Site Reactions [ISRs]), vital signs (blood pressure, pulse and orthostatic changes, and temperature), body weight and BMI, laboratory tests, ECG, concomitant medication use, time to all-cause discontinuation, all-cause discontinuation rates and discontinuation rates due to adverse events (tolerability), time to all discontinuation by reason, and safety rating scales (including Abnormal Involuntary Movement Scale [AIMS], Barnes Akathisia Rating Scale [BARS], Simpson-Angus Scale [SAS], C-SSRS, and CDSS).

Safety assessments and time points are provided in Table 1 (for Period 1) and Table 2 (for Period 2) of the study protocol.

The safety analysis will be performed separately for Period 1 and for the integrated study periods.

The safety analysis for Period 1 will be performed by treatment group and overall (total).

The safety analysis for the integrated study periods that will be presented in the CSR and in the IDMC closed reviews, will be performed by treatment group. Specifically, for IDMC closed reviews, patients rolling over from Placebo group will be distinguished from patients who continued their active treatment assignment from Period 1. Data from Period 1 for placebo patients will not be included in the integrated summaries.

For the open sessions of the IDMC reviews, data from Period 1 and from Period 2 will be presented separately. Summary tables will be generated for each period and will only be presented as a single total column.

For the following safety variables: Adverse events, Clinical laboratory results, ECG, weight and BMI and Vital signs, a separate safety summary will be presented for the 'While on Treatment' period, defined as the period between the first IMP administration visit until and including the End of Treatment visit (including the Early Termination visit if conducted during this period). In addition a separate safety summary table and listing will be presented for the Follow-Up period, defined as the period after the End of Treatment/Early Termination visit until the end of the study.

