8.6. Clinical Laboratory Tests

Clinical laboratory tests (serum chemistry, hematology, urinalysis) are detailed in Table 9 of the study protocol. Central laboratory value and changes from baseline will be summarized.

Laboratory test results will be presented in standard international (SI) units. Listings will include all laboratory values (central and local laboratories).

Laboratory test results will be presented for Period 1 and for the integrated study periods.

Summary statistics for chemistry, hematology and urinalysis laboratory tests will be presented at time points detailed in the Schedule of Assessment Table 1 and Table 2 of the study protocol.

Laboratory values and changes from baseline to each scheduled visit will be summarized using descriptive statistics.

Shifts (below, within, and above the normal range) from baseline to each scheduled visit including "at any visit" assessment (as a separate visit) will be summarized using patient counts. Summaries of potentially clinically significant abnormal values will include all post-baseline values (including scheduled, unscheduled, and withdrawal visits). The incidence of potentially clinically significant abnormal values will be summarized for laboratory variables using descriptive statistics with the criteria specified in [Table 2](#) below.

Summaries will be presented for the While on treatment period (starting from the baseline visit in Period 1 to the EOT visit, including ET visit if conducted during this period). A separate summary will be presented for the Follow-Up period (any visit conducted after EOT visit and until the end of the study).

Table 2: Criteria for Potentially Clinically Significant Laboratory Values

Test	Criterion value
Serum chemistry	
Alanine aminotransferase (ALT)	$\geq 3x$ ULN
Aspartate aminotransferase (AST)	$\geq 3x$ ULN
Alkaline phosphatase	$\geq 3x$ ULN
Lactate dehydrogenase (LDH)	$\geq 3x$ ULN
Blood urea nitrogen (BUN)	≥ 10.71 mmol/L
Creatinine	≥ 177 μ mol/L
Uric acid	≥ 625 μ mol/L
Men	
Women	≥ 506 μ mol/L
Bilirubin (total)	$\geq 2x$ ULN
Potassium	≤ 3 mmol/L ≥ 6 mmol/L
Calcium	≤ 1.5 mmol/L ≥ 3.5 mmol/L
Hematology	
Hemoglobin	≤ 115 g/L
Men	
Women	≤ 95 g/L
White blood cell (WBC) counts	$\leq 3 \times 10^9$ /L $\geq 20 \times 10^9$ /L
Absolute neutrophil counts (ANC)	$\leq 1 \times 10^9$ /L
Platelet counts	$\leq 75 \times 10^9$ /L $\geq 700 \times 10^9$ /L

ULN=upper limit of normal range.

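### The integrated by-visit safety tables reset former-placebo patients to a week 8 baseline but keep trial visits as the time axis, so each Period 2 dosing-visit row mixes patients 8 weeks and two injections apart

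*SAP*

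**What the plan says.** Four rules in the SAP act together on the integrated-period tables.

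- **Column (SAP 3.3).** "Patients that were randomized to Placebo in Period 1 will be counted according to the initial dose of TV-44749 they actually received" after re-randomization.
- **Baseline (SAP 4.2).** "For patients that were assigned to placebo group in Period 1, the baseline value is the baseline value for Period 2", which is the last value before the week 8 injection. SAP 8.1 also leaves these patients' Period 1 data out of the integrated summaries.
- **Time axis (SAP 4.4).** "Study days will be numbered relative to the first day of IMP administration (i.e., the first administration in Period 1"; for these patients that first administration was placebo. The same section adds: "For the by-visit summary tables, only scheduled visits, EOT and follow-up visits will be presented".
- **Content.** For the laboratory (SAP 8.6): "Laboratory values and changes from baseline to each scheduled visit will be summarized using descriptive statistics". Weight and BMI change (8.7), BARS (8.12.4) and CDSS (8.12.5) are likewise summarised by visit for the integrated periods. AIMS (8.12.2) and SAS (8.12.3) changes from baseline are summarised for the integrated periods too.

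The SAP separates the two kinds of patient elsewhere. In the IDMC closed reviews, "patients rolling over from Placebo group will be distinguished from patients who continued their active treatment assignment from Period 1" (SAP 8.1). The Period 2 PANSS summaries use six groups (SAP 6.4.1.2). Exposure counts from the first TV-44749 injection (SAP 8.2), and time to discontinuation counts from Period 2 randomization for former-placebo patients (SAP 9.2). No equivalent rule is visible for the integrated by-visit tables in the CSR.

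**The concern.** Column and baseline are both moved to the start of active treatment, but the row is not. A reader of the week 20 row in a dose column would take it as change after 20 weeks on that dose. For some of the patients in the row it is change after 12 weeks.

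Weight, BMI, HbA1c and lipids can be expected to depend on time on drug, and Period 2 exists to describe long-term safety. If these measures drift with exposure, the pooled by-visit mean is pulled towards the shorter exposure. The pull is strongest at the early Period 2 visits, and nothing in the table shows it. SAP 4.2 warns that placebo patients' baselines differ between the Period 1 and integrated tables, but it does not mention the mismatch in time.

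**Working it through.** **Schedule.** The protocol synopsis gives 2 injections in Period 1 (weeks 0 and 4) and up to 12 in Period 2 (weeks 8 to 52). At 4 weeks each, 2 + 12 = 14 injections and 14 × 4 = 56 weeks, which matches the stated maximum treatment duration. The SAP 8.2 exposure formula (last day − first day + 28) gives 52 × 7 + 28 = 392 days for a patient on active drug throughout and 44 × 7 + 28 = 336 days for a former-placebo completer. The gap is 56 days, or 8 weeks and two injections.

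**Share of each column.** Allocation is 1:1:1:1, then 1:1:1 for placebo patients. With week 8 retention p on placebo and a on active, the former-placebo share is s = (p/3) / (a + p/3).

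- Equal retention: s = (1/3) / (4/3) = 25%. At the planned 440 week 8 completers, that is 110/3 ≈ 37 of about 147 per column.
- Assumed 50% placebo, 80% active: s = 0.167/0.967 = 17%.
- Assumed 80% placebo, 60% active: s = 0.267/0.867 = 31%.

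The early-termination rate is redacted, so these are scenarios and not plan figures. Retention after week 8 is taken as equal.

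**Time on drug in each row.** At trial week w, continuing patients have w weeks and former-placebo patients have w − 8, so the mean is w − 8s. The shortfall is 8 × 0.25 = 2 weeks, with a range of 8 × 0.172 = 1.4 to 8 × 0.308 = 2.5 weeks. If a change is linear in time on drug, its mean is understated by 8s/w. Injections are those given before the visit's own dose.

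| Trial week | Continuing (weeks / injections) | Former placebo (weeks / injections) | Mean weeks at 25% | Understatement at 25% (17% to 31% share) |
|---|---|---|---|---|
| 12 | 12 / 3 | 4 / 1 | 10 | 16.7% (11% to 21%) |
| 20 | 20 / 5 | 12 / 3 | 18 | 10% (7% to 12%) |
| 32 | 32 / 8 | 24 / 6 | 30 | 6.3% (4% to 8%) |
| 44 | 44 / 11 | 36 / 9 | 42 | 4.5% (3% to 6%) |

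The week 12 row exists for weight, BMI and CDSS. Laboratory tests, AIMS, BARS and SAS are next done after visit 11 at week 20 (protocol Table 2), so week 20 is their first affected later row. At visit 11 itself, former-placebo patients are at their own baseline; if they are shown in that row, their change is zero by construction, beside patients with 8 weeks on drug.

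**Would re-indexing line the rows up?** Counted from the first TV-44749 injection, weight and CDSS fall on a common 4-week grid. Laboratory visits do not: continuing patients have weeks 4, 8, 20, 32, 44 and, for completers, 56, whereas former-placebo patients have weeks 12, 24, 36 and, for completers, 48. After week 0 the two series share no time point. In Period 2, AIMS, BARS and SAS follow the same 12-weekly pattern.

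**The case against.** The strongest reply is that the sentence on study days numbers days and does not define table rows, so the point rests partly on silence. That is fair as far as the sentence alone goes. The misalignment follows from the by-visit rule in the same section, from SAP 8.6, and from the lack of a re-mapping rule. Following those rules as written produces the mixed rows.

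A second reply is that rows are labelled by visit rather than by exposure, and that exposure is tabulated separately. This softens the point, but an exposure table does not let a reader undo the mixing in a by-visit mean. The further tables by exposure duration in SAP 8.1 are optional and would not re-index visits.

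Third, the tables are descriptive and the effect fades with time. Both are true and limit the weight of the point.

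A reader might also infer more than the documents support:

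- **Plasma concentrations.** Protocol 10.9 plans a table by sampling time and treatment group, but SAP section 10, which would govern, is redacted. How former-placebo patients are grouped there cannot be known.
- **A fixed 8-week gap at the end-of-treatment row.** That visit follows each patient's last dose, so the gap of 56 against 48 weeks holds for completers only.
- **Weight shifts.** SAP 8.7 uses screening as the reference for that table, so no baseline is reset. Only time on drug differs between patients at the same visit.

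**Conclusion.** The point holds for the integrated-period by-visit safety tables in the CSR: laboratory results including HbA1c and lipids, weight and BMI change from baseline, AIMS, SAS, BARS and CDSS. The 8-week, two-injection offset follows from the nominal schedule, before visit windows. The effect on a mean rests on three assumptions: the retention pattern, equal retention after week 8, and a change linear in time. If the change flattens with time, the percentages above are upper limits.

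The documents do not support reading this as a threat to the trial's efficacy conclusion or to its safety reporting as a whole. The primary analysis, the Period 1 safety tables, incidence summaries, summaries over all visits, exposure and time to discontinuation do not depend on this alignment. The change is worth making because the pooled rows can understate time-dependent change where it is of most interest, and the SAP already contains the better layout.

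**What to change.** In SAP 4.4 and 8.1, state that every integrated-period by-visit table in the CSR shows former-placebo patients in columns separate from patients who continued their Period 1 dose, as in the IDMC closed reviews. If pooled rows are also wanted for measures taken at every dosing visit, such as weight, index them by weeks since the first TV-44749 injection, with visit 11 as week 0 for former-placebo patients. Laboratory tables need the separate columns, because their visits do not align after re-indexing; AIMS, BARS and SAS are in the same position. Incidence tables can stay pooled.

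The cost is SAP wording and table programming, with no new data and no change in conduct. The tables become wider, and each former-placebo column would hold about 37 patients at the planned 440 week 8 completers, fewer if some do not enter Period 2.

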5. STUDY POPULATION

5.1. General

The full analysis set (Section 3.1) will be used for all study population summaries, unless otherwise specified. Summaries will be presented by treatment group, by period (Period 1 or Integrated periods, as specified) and overall (i.e., including a total column).

5.2. Patient Disposition

Definition	Disposition/Completion status
Randomized, not treated	A patient who was randomized but did not receive any injection
Period 1 Completer	A patient who completed all Period 1 scheduled injections and Visit 11 or completed Visit 10 and has PANSS total score in allowed window of Visit 11.
Period 1+2 Completer	A patient who completed all Period 2 scheduled injections and completed EOT visit assessments. If the sponsor decides to terminate the study earlier, patients who are terminated early due to this decision and has already received at least one injection in Period 2 and completed EOT visit, will be considered as Period 1+2 completers.
Study completer	Period 1+2 completer who completed FU visit
Early Terminated in P1	A patient who received at least one injection but terminated the study before week 8 (Visit 11).
Early Terminated in P2	A patient who was randomized to P2, received at least one injection, but terminated the study before Visit 22 or before the time point at which the sponsor decides to terminate the study, the earlier of the two dates.
Discontinued before EOT	Patient who received at least one injection and did not complete EOT visit
Discontinued before FU	A patient who received at least one injection, completed EOT, and did not complete follow-up visit
Follow-up Completer	A patient who received at least one injection and completed follow-up visit assessments

In the IDMC sessions, counts and percentages of ongoing patients in Period 1 and in Period 2 will be presented (i.e., Patients who did not terminate the study at the time of the data cut-off date).

Summary table of patient disposition will include the following:

- patients screened
- patients screened but not randomized and reason(s) for not being randomized
- patients who are randomized (full analysis set)
- patients randomized but not treated
- randomized and treated (safety analysis set)
- patient completion status as defined above; patients who were early terminated in Period 1 or in Period 2 or discontinued the study as described above will also be summarized by reason for discontinuation using descriptive statistics.

5.3. Demographics and Baseline Characteristics

Patient demographic and baseline characteristics (eg age, sex, race, ethnicity, height, weight, BMI, disease length, prior use of olanzapine, PANSS score at baseline, and region) will be summarized using descriptive statistics for the full and safety analysis sets. For continuous variables, descriptive statistics (number [n], mean, standard deviation, median, minimum, and maximum) will be provided. For categorical variables, patient counts and percentages will be provided. Categories for missing data will be presented, if necessary.

5.4. Medical History

All medical history data will be coded using the Medical Dictionary for Regulatory Activities (MedDRA version 26.0 or later version). The incidence of medical history abnormalities will be summarized using descriptive statistics by system organ class (SOC) and preferred term (PT). Patients will be counted only once in each PT and SOC category. Summaries will be presented by treatment group and overall (total) using the safety analysis set.

5.5. Prior Therapy and Medication

Any prior therapy, medication, or procedure a patient has had within 30 days before IMP administration and up to the end of study, including FU, will be recorded on the CRF. The trade name and international non-proprietary name (if available), indication, dose, and start and end dates of the administered medication will be recorded. The sponsor will code all medication according to the World Health Organization drug dictionary (WHODRUG GLOBAL B3 March 1, 2023 or later version).

The incidence of prior therapies and medications will be summarized using descriptive statistics by therapeutic class and preferred term. Patients are counted only once for each therapeutic class category, and only once for each preferred term category. Prior therapies and medications will include all medications taken and therapies administered before the first day of study drug administration.

